Title: Evaluating High Flow Humidification Therapy in Patients with Cystic Fibrosis

NCT #: NCT02129803

Document date: May 25, 2016

Document Type: Protocol and Statistical Analysis Plan

Evaluating High Flow Humidification Therapy in Patients with Cystic Fibrosis

Protocol Number: HM20002205
NCT02129803

Sponsor: Virginia Commonwealth University

Funding Support: Fisher & Paykel Healthcare

Investigators: [name], MEngr, MD,MBA, FRCPC (Principal Investigator)
H. [name] (Co-Principal Investigator)
[name], MPH (Sub-Investigator)
[name] (Sub-Investigator)
[name], MD (Sub-Investigator)

Sites: Children's Hospital of Richmond at VCU/VCU Medical Center
Main Hospital, 7th Floor – Pediatric Services
[name]
[name], United States

Children's Hospital of Richmond at VCU
Children's Pavilion
[name]
[name], United States

VCU Medical Center
Critical Care Hospital, 3rd Floor
[name]
[name], United States

VCU Health Systems
[name]
[name], United States

INTRODUCTION

Mucus secretion and clearance is the primary physical defence of the airway epithelium.¹ Although mucus plays a defensive role, secretion retention is a common but serious problem in patients with chronic lung disease such as cystic fibrosis (CF).³ Poor ion transport and rapid respiratory rate are thought to play a role in secretion hypohydration in the CF airway and this is thought to contribute to poor mucus clearance, increasing pulmonary symptoms (pulmonary exacerbation), poor sleep quality and a reduction in quality of life (QoL).⁴ We have recently shown that high-flow, heated and humidified air delivered by a nasal cannula (HHNC) improves mucociliary clearance and clinical outcomes in young children requiring chronic mechanical ventilation.⁵ To date, nocturnal HHNC (without supplemental oxygen) therapy has not been studied in individuals diagnosed with CF but previous laboratory research suggests that this could be safe and beneficial.⁶

HYPOTHESIS

It is hypothesized that HHNC delivered at 20 liters per minute (LPM) via Optiflow™ cannula and AIRVOT™2 device may favorably affect the physical properties of the sputum and improve the subject's ability to clear secretions, resulting in beneficial clinical effects and improved quality of life.

STUDY OBJECTIVES AND ENDPOINTS

Primary Objectives

- To evaluate the effectiveness of 20 LPM HHNC therapy (Optiflow™ cannula and AIRVOT™2 device) – experimental therapy versus 5 LPM HHNC therapy (Optiflow™ cannula and AIRVOT™2 device) – control therapy on physiological outcomes in hospitalized subjects with cystic fibrosis during an acute exacerbation.

Secondary Objectives

- To determine if the experimental therapy has an effect on Quality of Life as measured by the Cystic Fibrosis Questionnaire - Revised (CFQ-R) compared to control therapy
- To determine the effect of the experimental therapy on sleep duration using actigraphy (Actiwatch® 2) and subjective sleep quality measured by the Leeds Sleep Evaluation Questionnaire (LSEQ) compared to control therapy
- To determine the effect of the experimental therapy on Quality of Life in respect to nasal dysfunction as measured by the Sino-Nasal Outcome Test (SNOT-20) compared to control therapy
- To determine the effect of the experimental therapy on comfort and ease of use using the non-validated comfort survey (VAS score) compared to control therapy

Primary Endpoints

- Change in sputum volume, cough transportability and hydration (% solids)
- Change in FEV₁ % predicted from admission to end of study.

STUDY DESIGN

The study is a single-center, randomized pilot study to evaluate the clinical effectiveness 20 LPM HHNC (Optiflow™ cannula and AIRVOT™2 device) experimental therapy, versus 5 LPM HHNC (Optiflow™ cannula and AIRVOT™2 device) control therapy, on specified outcomes in hospitalized subjects with cystic fibrosis during acute exacerbation.

Potential subjects will be identified in clinic before admission to the Children's Hospital of Richmond at VCU (CHoR) or Virginia Commonwealth University Medical. If potential subjects are not identified in clinic, they will be introduced to and informed of the study by a member of the study team within 24 hours of hospital admission.

Assent from a subject will be obtained if they are aged 10 to 17 years along with informed consent from the eligible subject's parent or legal guardian. Informed consent will be obtained from subjects aged 18 years or older. All informed consent/assent discussions will take place in a private room and be documented according to the Pediatric Research Office's 'Informed Consent Process Cover Sheet'. Potential subjects and family members will be given as much time as necessary to determine if they would like to participate in the study. No study team member will be present during this period to minimize any possible coercion.

After informed consent is obtained the subject will be assigned a unique ‘Subject Identification Number.’ This number will consist of ‘VCUFP##’, where the first subject will be ‘VCUFP01’, the second ‘VCUFP02’, and so forth. This unique identifier will be used instead of the subject’s name, birth date, etc., to identify the subject for all study records and data.

After Subject Identification Number assignment is performed, randomization will occur. The study team will use the website www.randomization.com to randomize 30 study conditions (15 experimental and 15 control). The Study Coordinator will follow the randomization table chronologically as new subjects are consented.

This study is designed to accommodate 30 subjects (15 subjects per group) (Table 1). The study population will be determined from previously diagnosed CF patients who receive their CF care at CHoR and Virginia Commonwealth University. Subjects will be aged 10 years and older who are experiencing a CF exacerbation that requires hospital admission and therapy.

Table 1
STUDY DESIGN

Study Group	Assigned Intervention	Total Number of Subjects
Control Therapy	Low-Flow, 5 LPM (via Optiflow™ cannula) Heated (34°C), humidified air	15
Experimental Therapy	High-Flow, 20 LPM (via Optiflow™ cannula) Heated (34°C), humidified air	15

If a subject requests to withdraw from the study at any point, they are asked to inform the study doctor. Withdrawal from the study will not affect standard treatment the subject will receive for their CF exacerbation or ongoing treatment they may require. Upon withdrawal, the subject will forfeit any compensation for study participation.

Study subjects may be involuntarily removed from the study if the study doctor believes that they are not complying with the study protocol and/or the study doctor believes it is in the best interest of the subject to stop participation.

Study devices/equipment

The experimental therapy will be administered using Optiflow™ nasal cannula with the AIRVO™2 humidifier. The AIRVO™2 device will heat and humidify ambient air and the Optiflow™ nasal cannula will deliver the heated (approximately 34°C) and humidified air via the nares at a flow of 20 LPM.

Fisher & Paykel Healthcare manufactures the Optiflow™ nasal cannula and the AIRVO™2 device. The Optiflow™ nasal cannula and AIRVO™2 device are being provided by Fisher & Paykel Healthcare for the study with no cost to the study subject. In addition, the subject will not be subjected to any further costs associated with the study. The study devices will only be available for use by the subjects that are enrolled in the study. The subject will be required to return the study device at the conclusion of the subject’s study involvement, or when the subject is discharged from the hospital (whichever occurs first).

The control therapy will be administered using Optiflow™ nasal cannula with the AIRVO™2 device. The nasal cannula will deliver heated (approximately 34°C) and humidified air into the subject’s nares at a flow of 5 LPM. This aims to mask the experimental and control therapy from the subjects and investigators.

Subjects will be educated by the study coordinator on how the device works and how to set up the nasal cannula appropriately. Subjects will be instructed to sleep with the designated nasal cannula and device as instructed during their hospitalization, for a maximum of five nights. The time the device is placed in the subject's nares and the time when the device is turned on will be recorded regardless of the intervention group to which the subject is assigned. The nursing staff will be instructed to check that the individual is wearing the device (either experimental or control) appropriately throughout the entire night. Should the nursing staff notice the nasal cannula being worn incorrectly the nurse will attempt to correctly reposition without disturbing the subject or if this is not successful the subject will be awakened to ensure correct cannula placement. Following the overnight intervention, the nasal cannula will be removed from the device and washed with warm water and mild dish washing detergent. After rinsing with clean water the nasal cannula will be stored in a clean zip locked bag taped to the device during periods of non-use.

At study conclusion for each subject (Table 2. Study Procedures), the device will be cleaned and sanitized per manufacturer's guidelines. While not in use, the devices will remain clean/sanitized and stored appropriately within in the hospital facility.

Eligibility Criteria

Individuals must meet all of the inclusion criteria listed below in order to be considered as a potential study subject.

Inclusion Criteria:

- Confirmed diagnosis of CF
- Hospital admission for acute pulmonary exacerbation of CF
- 10 years of age or older
- Is able to comply with the procedures scheduled within the protocol
- Provide informed consent/assent

If an individual is eligible as defined by the inclusion criteria but is found to meet any of the exclusion criteria listed below, they will not be permitted to enroll in the study.

Exclusion Criteria:

- Receipt of any aerosolized experimental or investigational drugs within 1 month of enrollment
- History of ENT surgery, nasal bleeding or nasal polyps within 6 months of starting study
- Requires supplemental oxygen
- History of obstructive sleep apnea
- History of pressure headaches requiring therapy within 1 month of enrollment
- Other medical or psychological conditions in which the study doctor(s) believe(s) would inhibit the individual from being an appropriate study subject.
- Has any contraindications to HHNC as listed below:
 - Maxillofacial trauma
 - Complete nasal obstruction
 - Presence of suspected base of skull fracture
- Any contraindication that applies to CPAP/ NIV therapy

STUDY PROCEDURES

The study requires clinical observations and overnight intervention therapy for/up to the first 5 nights of hospitalization. The study procedures to be performed on/by each subject enrolled in the study are outlined in Table 2.

Table 2
STUDY PROCEDURES

Time point	Procedure/Assessment
SCREENING (Day 0) (In CF Clinic or within 24 hours of hospital admission)	
Admission into the Children's Hospital of Richmond or MCV Hospital for adult subjects (hospital).Introduction to study and review the study procedures/study device with the study coordinator and/or study doctorVerification of inclusion/exclusion criteria and signing of Informed Consent Document.Assignment of the unique Subject Identification NumberReview of medical history and treatment recordsBaseline tests (as part of standard of care as medically indicated)Completion of the Leeds Sleep Evaluation Questionnaire (LSEQ) by subject.Completion of the CF-specific health related quality of life survey (Cystic Fibrosis Questionnaire – Revised (CFQ-R) by subject.Completion of the Sino-Nasal Outcome Test (SNOT-20) by subject.Sputum sample collection (if possible)Randomization to intervention - either: 'Control Therapy' (Low Flow, heated and humidified air delivered at 5 LPM via Optiflow™ cannula and AIRVO™2 device) or 'Experimental Therapy' (High-Flow, heated and humidified air delivered at 20 LPM via Optiflow™ cannula and AIRVO™2 device)
BASELINE Day 1 (Approximately 9:00 AM)	
The device will be turned off (unless the subject has awakened earlier, in which case the subject can turn off the device when they wake).Sputum sample will be collected (where possible) or collection of previously produced sputum to research laboratory by study coordinator by 10:00 AM.Study coordinator will ensure that the nasal cannula is removed from the device and washed with warm water and mild dish washing detergent and rinsed thoroughly with clean water. The study coordinator will then place the nasal cannula in a clean zip locked bag taped to the device until required.Completion of the Leeds Sleep Evaluation Questionnaire (LSEQ)Completion of the device comfort survey (VAS Score).The study coordinator will collect the device log, and review the previous night's medical records (including any test results or medication dispensed).
TREATMENT PHASE Day 2 – 5 (PM)	
There will be no collection of produced sputum during this time.There will be no surveys completed during this time.The study coordinator and/or the study doctor will continue to review the subject's treatment and medication records.

Table 2
STUDY PROCEDURES

Time point	Procedure/Assessment
	
 Subjects will be allowed to go to sleep at whatever time they choose but must turn on the device before sleep onset and leave it on throughout the sleep period. The nursing staff will be instructed to ensure the subject continues to wear the device during the night. If for some reason the device comes off, or is turned off, the nurse will record the event and will attempt to correctly reposition without disturbing the subject or if this is not successful the subject will be awakened to ensure correct cannula placement. If the subject is discharged between Day 2 – Day 5, then the date of discharge will follow the 'Discharge' study procedure in place of the 'Treatment Phase' study procedure
DISCHARGE Day 6 (AM)* (*or earlier if discharged prior to 5 days of treatment)	
 The device will be turned off (unless the subject has wakened earlier), in which case the subject can turn off the device when they wake. Sputum sample will be collected (where possible) or collection of previously produced sputum to research laboratory by study coordinator by 10:00 AM. Subject will remove Actiwatch® 2 and Study Coordinator will download Actiwatch® 2 data Completion of the Leeds Sleep Evaluation Questionnaire (LSEQ) by subject Completion of the CF-specific health related quality of life survey (Cystic Fibrosis Questionnaire – Revised (CFQ-R) by subject Completion of the Sino-Nasal Outcome Test (SNOT-20) by subject Completion of the device comfort survey (VAS Score) by subject. The study coordinator will collect the device log, and review the previous night's medical records (including any test results or medication dispensed). A follow-up appointment in the CF clinic will be scheduled according to the study doctor's recommendations (as part of standard care). The subject will be reminded to call the study coordinator or the study doctor if there are any new problems, questions or concerns once discharged from the hospital.
Clinical Follow-up Appointment	
 The study coordinator and/or the study doctor will review the medical history and treatment records. Baseline tests (as part of standard of care as medically indicated) Completion of the Leeds Sleep Evaluation Questionnaire (LSEQ) by subject Completion of the CF-specific health related quality of life survey (Cystic Fibrosis Questionnaire – Revised (CFQ-R) by subject Completion of the Sino-Nasal Outcome Test (SNOT-20) by subject Sputum sample collection (if possible). The sputum will be delivered to the research laboratory by the Study Coordinator Study compensation

DATA HANDLING AND RECORD KEEPING

Power Calculation

No studies have evaluated the effect of high-flow HHNC therapy to improve sinopulmonary symptoms in CF. Thus, the current study is designed as a pilot study that is likely to be underpowered to reach significance.

Electronic Database Capture

Study data will be collected and managed using REDCap (Research Electronic Data Capture). REDCap is a secure web application designed to support data capture for research studies, providing user-friendly web-based case report forms, real-time data entry validation (e.g. for data types and range checks), audit trails and a de-identified data export mechanism to common statistical packages (JMP, SAS). REDCap also includes a powerful tool for building and managing online surveys. The database is hosted by VCU under award number UL1RR031990 from the National Center for Research Resources and NIH Roadmap for Medical Research, National Institutes of Health.

Only the study coordinators and the research assistants will have access to this password protected database.

With the exception of the ‘Informed Consent/Assent’ pages in the REDCap database, all subsequent pages will only identify the subject by the Subject Identification Number.

All hard copies of the signed Informed Consent/Assent documents will be kept in locked cabinet which is located in the study coordinator’s locked office. A copy of the signed Informed Consent/Assent will be scanned into the subject’s electronic medical record. Any other paper records that may be generated during the course of the study will be de-identified and labeled with the individuals Subject Identification Number and kept separated from the consent forms and locked in a cabinet in the study coordinator’s locked office.

OnCore

OnCore is a clinical trial management systems (CTMS) which will be used for recording and tracking regulatory approvals, staff training and safety management (SAE tracking and IRB reporting). The CTMS system was developed by Forte Research and widely used across academic research universities nationwide. The program is a secure web-based system hosted by both the VCU and MCV health systems. Only fully-trained, credentialed employees of VCU have access to this database. The study coordinator will be the only individual (besides individuals that manage OnCore) with access to data entered for this study into the OnCore database.

SPUTUM SAMPLE COLLECTION AND PROCESSING

Sputum collection is needed for evaluation of biophysical properties.

The study coordinator will ask the study subject to cough sputum into a provided, sterile sample cup at 9:00 AM according to the schedule of events outlined in Table 2. Study Procedures. If the subject is able to produce sputum before this time, they will be provided the sterile sample cup and the sputum collected. All sputum samples will be transported on ice to the research laboratory as soon as possible on the day of screening and at follow-up. At baseline, intervention, and discharge, sputum will be delivered to the research laboratory on ice by 10:00 AM.

All sputum samples will be identified by the Subject Identification Number and the applicable time-point only.

SPUTUM SAMPLE ANALYSIS

All collected sputum samples will be used for cough transport and mucus hydration measurements.

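### The primary sputum change has no stated start or end visit, and the only Table 2 row labelled BASELINE appears to follow a night on the assigned device

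*Combined protocol and SAP*

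**What the plan says.** All references are to the combined protocol and SAP.

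- **Primary Endpoints.** The sputum bullet reads "Change in sputum volume, cough transportability and hydration (% solids" and names no visit. The separate FEV₁ bullet does carry a window, "predicted from admission to end of study".
- **Data Analysis.** This section names t-tests, ANOVA and the 0.05 level. It defines no reference visit, end visit or change score.
- **Table 2, Screening (Day 0).** Optional sputum is listed just ahead of randomisation: "Sputum sample collection (if possible)Randomization to intervention - either".
- **Table 2, the row headed** "BASELINE Day 1 (Approximately 9:00 AM". Its first step is "The device will be turned off (unless the subject has awakened earlier". Sputum is conditional here as well: "Sputum sample will be collected (where possible". A later step is "Completion of the device comfort survey (VAS Score).The study coordinator will collect the device log", together with a review of the records from the night before.
- **Study Procedures, opening text.** The study involves "overnight intervention therapy for/up to the first 5 nights of hospitalization".
- **Table 2, Discharge and Clinical Follow-up Appointment.** Sputum is collected again at both, subject to the subject being able to produce it.
- **Sputum Sample Collection and Processing.** Screening and follow-up samples go to the laboratory as soon as possible. Samples at baseline, intervention and discharge must arrive by 10:00 AM. Baseline is therefore a different sample from screening, and its delivery rule matches the Day 1 row.

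**The concern.** A change score is defined by its two end points, and this primary endpoint has neither. Two competent analysts could take the same data and report different primary sputum results, both consistent with the text.

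The one label that seems to settle the reference points to a sample that looks already exposed to 5 or 20 LPM. A reference taken after randomisation, under the assigned treatment, removes part of the treatment effect from the comparison. The resulting estimate of the full effect is too small if the first night's difference has the same direction as the final one, and too large if it has the opposite direction. In a pilot, whose estimate and SD may be used to plan a later trial, the choice of definition matters even where no test reaches significance.

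The Day 1 label does not affect FEV₁, which has its own window, or CFQ-R and SNOT-20, which are not collected on Day 1.

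**Working it through.** The plan gives no effect size, SD or power for sputum, so there is no figure to reproduce.

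**1. Count the definitions.** There are two possible references (Day 0, Day 1) and two possible end visits (discharge, follow-up): 2 × 2 = 4 definitions for each sputum measure. Day 0 to Day 1 is a fifth pair if Day 1 is allowed as an end visit. The text selects none.

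**2. Is Day 1 on-treatment?** No sentence says so outright. The inference rests on these steps, read together:
- randomisation is in the Day 0 row;
- the Day 1 row opens with the device being switched off on waking;
- subjects then rate device comfort;
- the device log is collected and the previous night's records are reviewed;
- therapy covers the first nights in hospital.

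The night count is only partly consistent. The evenings of Days 2 to 5 give 4 nights. Adding the night before Day 1 gives 5, the stated maximum, but leaves the Day 1 evening unassigned. Counting every night from Day 0 to Day 6 gives 6. These passages must be reconciled.

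**3. What a Day 1 reference does.** Write D0, D1 and D6 for the sputum values on Day 0, on Day 1 and at discharge:

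(D6 − D1) = (D6 − D0) − (D1 − D0)

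Taking the difference between arms, the Day 1 version equals the Day 0 version minus the between-arm difference in first-night change. This is an identity and needs no assumed effect. The size of the last term is not in the documents.

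**4. Would the data reveal it?** With 15 per arm and complete samples, the 95% CI half-width for the between-arm difference in D1 − D0 is t(0.975, 28) × √(2/15) = 2.048 × 0.365 = 0.75 SD of that change. An observed first-night shift smaller than this would not stand out from chance.

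**5. Leaving the choice open (illustration only).** For any single definition fixed in advance, type I error is 5% when there is no effect at any time. If the better of the two references were chosen after the data were seen, with discharge as the end visit, the rate for one sputum measure would depend on the correlation r between the two change scores. With equal variances,

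r = (1 − ρ(D0,D6) − ρ(D1,D6) + ρ(D0,D1)) / √[2(1 − ρ(D0,D6)) × 2(1 − ρ(D1,D6))].

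Simulated null trials (15 per arm, normal data, two-sided t-test at 0.05) give:

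| Assumed ρ(D0,D1), ρ(D0,D6), ρ(D1,D6) | r | At least one significant |
|---|---|---|
| 0.5, 0.5, 0.5 | 0.50 | about 9% |
| 0.9, 0.5, 0.5 | 0.90 | about 7% |
| 0.98, 0.5, 0.5 | 0.98 | about 6% |
| 0.3, 0.6, 0.6 | 0.125 | just under 10% |

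The correlations are assumptions and the rows are examples, not limits. The general ceiling is 2 × 5% = 10% for two definitions and 4 × 5% = 20% for four. Two of the patterns tried for all four definitions gave 9.5% and about 16%.

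**The case against.** **Day 0 is the natural reading.** This stands as a matter of likely intent. No text makes Day 1 the reference, and the neighbouring FEV₁ window starts at admission. The word baseline is also used loosely: Table 2 lists baseline tests in both the Day 0 and the follow-up rows. A reader might infer that the plan prescribes a contaminated baseline; the documents do not support that. They leave the choice open and attach the label to the wrong-looking visit. The end visit is open on any reading.

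**A table row may have been lost in extraction.** This also stands. Discharge has the Actiwatch removed, but no row puts it on. No row covers the Day 1 evening. The intervention sputum in the sputum section matches no row, and Table 2 rules out collection on Days 2 to 5. Some steps now under Day 1 could belong elsewhere. That lowers confidence in the Day 1 exposure. It would not supply the window that is absent from Primary Endpoints and Data Analysis.

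**Day 0 may not be clean either.** A reader might infer this because Study Design says only that randomisation follows number assignment. The inference is weak: Table 2 places Day 0 sputum under screening and ahead of randomisation, and Study Design does not contradict that order.

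**It is a pilot.** The Power Calculation section says the study is likely to be underpowered, so a claimed loss of power carries little weight. The objection does not reach the definition of the estimate, and the plan still tests at 0.05.

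**Day 1 is the better-matched sample.** Day 1 and discharge share the same morning procedure, while Day 0 has no fixed hour and may be taken in clinic. This is a real cost, most of all for volume. It is a reason to report Day 1 to discharge as a sensitivity analysis, not to make a probably exposed sample the primary reference.

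**Conclusion.** The concern holds in two parts, with different confidence.

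- **High confidence:** the primary sputum change has no reference visit and no end visit anywhere in the text, and at least four definitions fit.
- **Moderate confidence:** the Day 1 row labelled BASELINE follows a night on the assigned device. This is inferred from that row's steps in a table that may be incomplete.

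If the label is followed, the estimate omits the between-arm difference in first-night change. The documents do not allow its size to be derived.

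Two stronger conclusions are not supported. The first is that type I error is inflated: that requires choosing the definition after seeing the data, which nothing in the documents indicates, and the rates shown are illustrative. The second is a specific loss of power: any such figure would rest on an invented effect size, so none is given.

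This should be fixed. It concerns a primary endpoint, but a pre-device sample is already scheduled and clearer wording resolves it.

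**What to change.** 1. In Primary Endpoints, state that sputum change runs from the Day 0 sample, taken before first device use, to the Day 6 (or earlier discharge) sample, and that follow-up sputum is secondary.
2. In Table 2, relabel the Day 1 row as an on-treatment assessment and state that it is not the primary reference. A Day 1 to discharge comparison can be reported as a labelled sensitivity analysis.
3. In Sputum Sample Collection and Processing, use the same visit names as Table 2, and reconcile the intervention sample with the absence of collection on Days 2 to 5. While doing so, check Table 2 against the source document for a missing row, and reconcile the Day 1 evening with the five-night maximum.

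**Cost.** Wording only; no new visit or sample. The downside is that Day 0 sputum is collected only if the subject can produce it and at no fixed hour, so some change scores will be missing or noisier. As an assumed example, if 3 per arm lacked a Day 0 sample, the CI half-width would rise from 0.75 SD to t(0.975, 22) × √(2/12) = 0.85 SD. Day 1 sputum is conditional too, so using it as the reference would not remove missing data.

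### Subject numbers run in the same order as the allocation list and label the sputum tubes, with no stated limit on who sees the list, so masking of two primary laboratory readings is not assured

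*Combined protocol and SAP*

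**What the plan says.** **Numbering.** STUDY DESIGN gives each subject a number after consent, "where the first subject will be ‘VCUFP01’, the second ‘VCUFP02’, and so forth". This number stands in for the subject's identity, "to identify the subject for all study records and data".

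**Allocation.** The same section continues: "After Subject Identification Number assignment is performed, randomization will occur". On the list itself: "The study team will use the website www.randomization.com to randomize 30 study conditions", split 15 and 15. On its use: "The Study Coordinator will follow the randomization table chronologically as new subjects are consented".

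**Sample labels.** SPUTUM SAMPLE COLLECTION AND PROCESSING says: "All sputum samples will be identified by the Subject Identification Number and the applicable time-point only".

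**Masking.** Under Study devices/equipment, both arms use the same cannula and humidifier, and the stated purpose is: "This aims to mask the experimental and control therapy from the subjects and investigators". Laboratory staff are not mentioned.

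**What is read in the laboratory.** Primary Endpoints lists change in sputum volume, cough transportability, % solids and FEV₁ % predicted. SPUTUM SAMPLE ANALYSIS describes the bench work for cough transportability and % solids. It does not say who does that work or whether they are masked.

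**The concern.** Two sequences that ought to be unrelated, the subject number and the allocation row, are driven by the same event: the order of consent. Anyone who has seen the list needs no separate key to learn a subject's arm. The number on the tube is enough.

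This matters most for the primary outcomes read at the bench. Cough transportability is a distance in mm, measured after a 40 µl sample has been laid by hand in a thin line, so the reader's handling and measurement can influence it. % solids leaves less room, because it comes from microbalance weights before and after drying. A reader who knew the arm could, without intending to, shift the comparison between arms.

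The point is confined to the reading of laboratory outcomes. Concealment of the next assignment and the coordinator's contact with subjects are separate matters.

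**Working it through.** **Step 1. Does the number match the row?** Both start at 1 and advance by one at each consent. If every consented subject takes the next row, subject n uses row n, so the match is 30 of 30.

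That condition could fail. Table 2 lists number assignment well before randomization on Day 0, so a consented subject could receive a number and use no row. Suppose k numbers are skipped at random before the last randomized subject. There are then 29 + k positions in which the skips can fall. Number and row agree only for subjects before the first skip, and the expected count of those is (30 + k)/(k + 1) − 1.

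| Skipped numbers k | Expected exact matches | Share of 30 |
|---|---|---|
| 0 | 30 | 100% |
| 1 | 31/2 − 1 = 14.5 | 48% |
| 2 | 32/3 − 1 = 9.67 | 32% |
| 3 | 33/4 − 1 = 7.25 | 24% |

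A simulation of 20,000 runs gave the same shares. The exact match falls quickly, but order is preserved, so the list together with an enrolment log still gives the arm.

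**Step 2. What does the label reveal without the list?** Nothing. The allocation is 15:15, so a guess is right half the time. Knowing one subject's arm moves the chance that another is in the opposite arm only to 15/29 = 51.7%. The exposure therefore depends on access to the list.

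**Step 3. Who has access to the list?** The documents attribute its generation to the study team and its use to the coordinator. They do not say who keeps it, whether access is restricted, or whether the people who run the cough machine and weigh the samples belong to the team that made it.

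**Step 4. What would a reading bias do?** The plan gives no SD or effect size, so this is illustration with assumed shifts. Data Analysis specifies a two-tailed t-test at p < 0.05. With n per arm, a spurious shift of d SD and no true effect, the rejection probability is that of a noncentral t with 2n − 2 degrees of freedom and noncentrality d√(n/2). For n = 15 there are 28 degrees of freedom and the critical value is 2.048. At d = 0.25, for example, the noncentrality is 0.25 × √7.5 = 0.685.

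| Assumed shift (SD) | False-positive rate, 15 per arm | False-positive rate, 10 per arm |
|---|---|---|
| 0 | 5.0% | 5.0% |
| 0.1 | 5.8% | 5.5% |
| 0.25 | 10.1% | 8.3% |
| 0.5 | 26.2% | 18.5% |

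The second column is shown because Table 2 collects sputum only where possible, so fewer than 15 per arm may contribute; 10 is an assumption.

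The plan has no sample-size derivation to reproduce. The only related arithmetic, 15 + 15 = 30, agrees across the list, the text and Table 1.

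**The case against.** A reader might infer that the primary laboratory readings are unmasked, or that the labelling rule itself removes the mask. The documents do not support either statement. The tube shows no arm, the protocol states an aim to mask investigators, and nothing says that a laboratory reader has seen the list. Naming the study team as the source of the list is compatible with one person having generated it. This objection stands in full, and it is why the point is about assurance and not about a known breach.

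It can also be said that sequential numbers are harmless when the list is locked away. That is correct. The weakness lies in the combination: matched order, the same number on the tubes, and silence on custody of the list and masking of readers.

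Other limits also stand:

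- The cough-transport procedure fixes sample volume, depth and tank pressure and averages three readings, and % solids has a numerical density check of 1.00 ± 0.15. Room for judgement is limited, above all for % solids.
- Actigraphy carries the same number, but the software is on the coordinator's computer, and the coordinator already follows the allocation list. The label adds nothing there.
- The visual check of normality raises the question of masked analysis, which is separate from how tubes are labelled.
- The larger shifts in the table have no source in the documents. At 0.1 SD the effect is close to nominal.
- Power Calculation describes a pilot that is likely to be underpowered. This lowers the stakes but does not remove them, because the plan still tests at p < 0.05.

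**Conclusion.** The point holds as a gap in safeguards. As written, the subject number tracks the allocation row, exactly if no number is skipped and in order otherwise. That number is on every sputum tube, and nothing restricts the list or masks the reader. Masking of cough transportability and % solids, two of the four primary variables, is therefore not assured, and this sits uneasily with the aim to mask investigators. The risk is greater for the cough-transport distance than for % solids.

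The size of any bias cannot be derived from the documents. The false-positive rates above rest on assumed shifts and on the number of subjects who supply sputum. FEV₁ % predicted, also primary, is outside the point. No sample size, power or alpha figure changes. This is a cheap improvement worth making, not evidence that the results would be biased.

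**What to change.** 1. In SPUTUM SAMPLE COLLECTION AND PROCESSING, replace the subject number on laboratory tubes with a random code unrelated to consent order. The coordinator keeps the key, and results are linked to subjects only after the readings are entered.
2. In STUDY DESIGN, name who holds the allocation list, and restrict it to the coordinator or another person who neither reads sputum nor analyses data. If the coordinator holds both list and key, the coordinator should not take the readings.

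Hiding the visit on the tube, and analysing with arms coded X and Y, are optional extras. The point does not depend on them.

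The cost is one pre-printed code sheet, a sentence or two in each section, and a linking step that carries a small risk of mixing up samples if the key is poorly kept. Sample size, study visits and clinical care are unaffected.
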